6.4 Safety Evaluation

- (1) Evaluation Indicators
 - 1) Adverse events;
 - 2) Vital signs: including temperature, respiration, pulse, systolic blood pressure, diastolic blood pressure;
 - 3) Laboratory Check: Blood routine:
 - 4) Effects on the skin of the covered area, e.g. local infection, local skin irritation.
- (2) Evaluation method

Safety analysis was performed using the safety analysis population (SS).

The adverse event was coded according to the latest edition of the Medical Dictionary for Regulatory Activitie (MedDRA). Adverse events that occurred prior to randomization will be listed in the list only.

The analysis of AE will be based on Treatment Emergent Adverse Event (TEAE) during the treatment period. Any AE after the first application of the investigational device, whether or not related to the investigational device, will be defined as a TEAE, as will an AE that existed prior to the application of the investigational device but that worsens during the treatment period. In cases where AE cannot be defined as occurring before the first application of the investigational device or after the first application of the investigational device of the investigational device, AE will be classified as occurring after the first application of the investigational device as the most conservative approach.

The number of cases, case times, and percentages of all TEAEs, TEAEs belonging to CLABSI, TEAEs belonging to CRBSI, and TEAEs occurring in association with the investigational device are tabulated and summarized by system organ (SOC), preferred term (PT), and severity, respectively, for each group. Multiple occurrences of the same adverse event in the same participant will be summarized using the most severe one for severity and relevance to the investigational device.

TEAEs leading to study discontinuation, serious adverse events, and adverse events leading to death were summarized for each group by system organ (SOC), preferred term (PT), respectively, in descending order of the number of cases occurring in the test group.

Adverse events associated with the investigational device included a relationship to the investigational device determined to be: "relevant", "may be relevant".

Adverse events that led to study discontinuation included the choice of measures taken for the investigational device as: "Permanent deactivation of the investigational device".

All adverse events during the study, adverse events leading to study discontinuation, adverse events leading to death and serious adverse events will be detailed in the list.

Describe separately vital signs and baseline variation at the baseline and the last (i.e., end of treatment or withdrawal from discontinuation visit) visit and compare the two groups with t-test.

All tests completed at the last visit and descriptive statistics were listed for laboratory examination in the form of a pre- and post-treatment cross-tabulation (normal/abnormal results determined according to the range of normal values). A list of laboratory examination that appear abnormal after treatment, including random number, treatment group, test time point, item, measured value, and normal value range.

Qualitative descriptive statistics were used to describe separately erythema, erythema, pruritus score and skin infection at the baseline and last (i.e., end of treatment or withdrawal discontinuation visit) visit at different insertion sites in two groups and compare the two groups using the chi-square test or Fisher's exact test.

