19.4 Statistical Analyses

For patient baseline characteristics and demographic data, quantitative data will be analyzed based on t-test or rank sum test, and qualitative information will be analyzed based on Chi-square test or Fisher's exact test. CVC tip bacterial colonization rates, PICCO/hemodialysis catheter bacterial colonization rates, catheter-related bloodstream infection rates, and microbial species analysis will be analyzed by chi-square test or Fisher's exact test. Other results collected in this study, such as wearing duration, frequency of replacement, skin condition, and number of deaths, will be analyzed using t-tests or rank sum tests accordingly. The O'Brien-Fleming expenditure function will be used twice in succession to determine the test boundaries.

In addition, descriptive summaries of effectiveness and safety evaluation indicators will be presented for the entire trial and for subjects in each group. For continuous data, the data will be summarized by number of subjects, mean, standard deviation (SD), median, minimum and maximum values. For categorical data, they will be summarized by frequency and corresponding percentage.

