3.2 Study Population and Sample Size

440 subjects who meet the inclusion/exclusion criteria will be enrolled. Subjects will be adult voluntary clinical subjects, of either sex, at least 18 years of age, who are ICU patients undergoing deep venous catheterization (DVC), in which a CVC catheter must be used while other types of catheters such as hemodialysis, PICCO, and floating catheters may be used concurrently.

This study will use a positive two-sided Z test for continuity calibration and use the O'Brien-Fleming expenditure function to determine the test boundary. Assuming a baseline value of 18.7% for CVC tips colonization rate in the control group (this figure is reported by a domestic epidemiological survey) and a reduction rate of 50.0%, each group should contain at least 220 patients with CVC to reach an 80% likelihood at 5% significance level. A total of 440 valid cases are required in both groups combined. An interim analysis is scheduled for this study and will be conducted after completion of follow-up visits of 220 subjects to correct for the pre-defined sample size.

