4.2 Safety indicators

- (1) Adverse events;
- (2) Vital signs: Including temperature, respiration, pulse, systolic blood pressure, diastolic blood pressure, and study time point: Screening and enrollment, withdrawal/discontinuation of visits or end-of-treatment visits.
- (3) Laboratory Check: Blood routine includes red blood cell count, white blood cell count, platelet count, neutrophil %, neutrophil count, lymphocyte %, lymphocyte count, hemoglobin, C-reactive protein, and study time point: Screening and enrollment, withdrawal/discontinuation of visits or end-of-treatment visits.
- (4) Effects on the skin of the covered area, e.g. local infection, local skin irritation

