6. STATISTICAL ANALYSIS METHODS

6.1 General Principles

Statistical analyses will be performed using SAS 9.4.

In accordance with the O'Brien-Fleming expenditure function, all statistical tests in the final analysis were two-sided, and a p-value of less than 0.048 would be considered statistically significant for the difference being tested (except where specially described).

The description of quantitative indicators will calculate the number of cases (missing), mean, standard deviation, median, minimum, and maximum. The minimum and maximum values will have the same decimal digits retained as the raw data, but the mean, standard deviation, and median will have one more decimal digits than the raw data. However, generally the maximum number of raw data will not exceed four decimals.

The description of qualitative indicators will use the number of cases and percentages of each category. Calculation of percentage was based on non-missing data in the analysis set. Percentage was rounded to one decimal number. Unless special instruction, percentages will be calculated using the number of people in the corresponding group for each population as the denominator.

All numerically derived variables will keep two decimals, unless otherwise specified.

The treatment of missing data will be described in a separate section, otherwise all missing data will not be filled.

Missing days in the date will be filled using 1 day, and missing months will be filled using 1 month, as a general principle for filling missing dates, unless special instruction.

Baseline will be defined as the last test value prior to treatment.

Change relative to baseline in this paper will be defined as post-treatment minus baseline.

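### SAP 6.4 specifies only a normal/abnormal before-and-after table for the continuous blood results, with no between-arm comparison, and compares vital signs by t-test where a baseline-adjusted analysis would be more precise

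*SAP*

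**What the plan says.** SAP 4.2 makes routine blood tests one of four safety indicators. It begins the list with "Blood routine includes red blood cell count, white blood cell count, platelet count, neutrophil %, neutrophil count" and adds lymphocyte percentage and count, hemoglobin and C-reactive protein (CRP): nine items, all quantitative. Vital signs are another indicator, with five items. Both sets are measured at screening/enrollment and at the end-of-treatment or withdrawal visit.

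SAP 6.4 handles the measured indicators in three ways:

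- **Vital signs.** The values and their variation from baseline are described at baseline and at the last "visit and compare the two groups with t-test".
- **Blood results.** They are shown "in the form of a pre- and post-treatment cross-tabulation (normal/abnormal results determined according to the range of normal values"). A listing follows of results abnormal after treatment, with treatment group, measured value and normal range. No between-arm comparison is named.
- **Skin scores.** They are compared between arms by chi-square or Fisher's exact test.

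Protocol 19.4 says of effectiveness and safety indicators, overall and by group: "For continuous data, the data will be summarized by number of subjects, mean, standard deviation (SD), median, minimum and maximum values". SAP 6.1 gives a similar general rule for describing quantitative indicators and defines change as the post-treatment value minus baseline.

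**The concern.** Blood results are the only one of these three indicators for which SAP 6.4 names no comparison of the arms. The form it does name discards information in two ways. First, abnormal covers both directions, so a white cell or platelet count that moves from below the range to above it appears as unchanged. Second, a value already abnormal at baseline can worsen and stay in the same cell. That is probably common in intensive care patients, although the documents give no figure.

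For vital signs, the sentence does not say whether the t-test applies to the last value, to the change, or to both. None of these uses baseline as a covariate.

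What is at stake is how the safety tables are read. A normal/abnormal table that looks alike in the two arms could be taken as reassurance about white cells, platelets or CRP that it is too coarse to give.

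**Working it through.** **The plan's own figure.** The documents state no effect size, SD or power target for blood results or vital signs. The only sample-size figure concerns catheter-tip colonization: "each group should contain at least 220 patients with CVC to reach an 80% likelihood at 5% significance level". It matters here only as the source of 220 per arm. With control rate 0.187 and a 50% reduction to 0.0935, n = [z(α/2)·√(2·p̄·(1−p̄)) + z(β)·√(p1(1−p1)+p2(1−p2))]² / (p1−p2)², where p̄ = 0.14025. At alpha 0.05 this is (1.960 × 0.4911 + 0.8416 × 0.4866)² / 0.0935², which rounds up to 216. At alpha 0.048 it is 219. So 220 reproduces without a continuity correction; with one the figures are 237 and 239. That does not bear on this point.

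**Inputs for vital signs**

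- From the documents: n = 220 per arm (SAP 3.2), and two-sided testing where "a p-value of less than 0.048 would be considered statistically significant for the difference being tested" (SAP 6.1), so z = 1.977.
- Assumed: a true shift of 0.27 SD, chosen because a t-test on the last value then has 80% power; a before/after correlation r of 0.3, 0.5 or 0.7; equal SDs at both times and in both arms; all 220 per arm with both measurements.

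**Formula.** Power = Φ(0.27 / (s·√(2/220)) − 1.977). Here √(2/220) = 0.0953, so 0.27/0.0953 = 2.832. The residual SD s, in units of the last-visit SD, is 1 for the last value alone, √(2(1−r)) for the change and √(1−r²) for ANCOVA.

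| r | s, change | Power, change | s, ANCOVA | Power, ANCOVA | Power, last value |
|---|---|---|---|---|---|
| 0.3 | 1.183 | Φ(2.393 − 1.977) = 66% | 0.954 | Φ(2.969 − 1.977) = 84% | 80% |
| 0.5 | 1.000 | Φ(2.832 − 1.977) = 80% | 0.866 | Φ(3.270 − 1.977) = 90% | 80% |
| 0.7 | 0.775 | Φ(3.656 − 1.977) = 95% | 0.714 | Φ(3.965 − 1.977) = 98% | 80% |

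The variance ratio of change to ANCOVA is 2/(1+r): 1.54, 1.33 and 1.18. ANCOVA is never worse than either t-test under this model. Its advantage over the change score shrinks as r rises, and its advantage over the last value grows.

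**Blood results, purely illustrative.** The SAP plans no test of the normal/abnormal table, so the following only measures the information lost by the cut. Keep 220 per arm, alpha 0.048 and a 0.27 SD shift in a normally distributed marker. The measured scale has 80% power. A two-proportion test of one-sided abnormality, with the shift toward abnormal, would have 41%, 58% or 61% if 10%, 30% or 50% of controls were abnormal. If abnormal pools 10% low with 40% high, power would be 15% for a downward shift and 28% for an upward one. With 25% on each side it would be 6%. All these abnormal fractions are assumed.

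**The case against.** The strongest reply is that the plan contains more than a quick reading suggests. Much of that reply stands.

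- **Vital signs and baseline.** A reader might infer that vital signs are tested without any use of baseline. The documents do not support that. SAP 6.4 names variation from baseline in the sentence that names the t-test, and SAP 6.1 defines change. Baseline very probably enters through the change score. What remains is efficiency, plus uncertainty about which quantity is tested.
- **Continuous blood summaries.** A reader might infer that none will be produced. The laboratory sentence mentions descriptive statistics, and SAP 6.1 and Protocol 19.4 both set mean, SD and median as the rule for continuous data. The tables are in a separate file (SAP 9). These summaries may therefore appear by arm, but SAP 6.4 ties its laboratory sentence to the cross-tabulation and does not settle it. The listing separates low from high, but only for results abnormal after treatment, so it cannot show a shift between arms.
- **A protocol requirement to test.** Protocol 19.4 assigns other collected results to t-tests or rank sum tests, but its examples do not include laboratory values. It is weak support for a required laboratory test.
- **Clinical weight.** White cells, neutrophils and CRP are not the only systemic signs of inflammation collected. Temperature, pulse and respiration are measured at the same visits and compared between arms. Suspected bloodstream infection and skin infection are compared directly, and Protocol 11.3 counts abnormal laboratory findings as adverse events.
- **Extra comparisons.** Nine blood items and five vital signs make 14 adjusted estimates for a product that Protocol 3.3.1 regards as low risk. This is a fair caution, and it argues for estimates with intervals rather than more significance tests.

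**Conclusion.** The point holds in a limited form. For continuous blood results, the only form of summary that SAP 6.4 spells out is a normal/abnormal cross-tabulation that pools low with high and names no between-arm comparison. For vital signs it plans an unadjusted t-test, where ANCOVA would be more precise at no cost in data. Against a change-score t-test, the illustrative gain is 18, 10 and 2 points of power at correlations 0.3, 0.5 and 0.7 (the last from unrounded 95.3% and 97.7%). This rests on an assumed shift of 0.27 SD, assumed correlations and complete data on 220 per arm.

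No comparable figure can be given for the planned blood analysis, because no test is planned; the dichotomized figures show only the direction and possible scale of the loss. The effect is confined to secondary safety summaries. The primary endpoint and its analysis are untouched. This is a worthwhile improvement, not a flaw that threatens the trial's conclusions.

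**What to change.** Amend SAP 6.4 as follows:

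1. **Blood results.** Summarize each item by arm on its measured scale: n, mean, SD, median, minimum and maximum at baseline and last visit, and the change. Report a baseline-adjusted between-arm difference with its confidence interval, on the log scale for skewed items such as CRP. Label these as descriptive safety estimates without multiplicity control.
2. **Cross-tabulation.** Keep it, but as low/normal/high before and after, by arm.
3. **Vital signs.** Replace the two-sample t-test with ANCOVA of the last value on group and baseline, and report the adjusted difference with its interval.

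The cost is SAP wording and a few table shells. The measured values, normal ranges and baseline measurements are already collected. The downside is a few more nominal safety intervals to interpret, some of which will exclude zero by chance.

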5.2 Secondary Objective(s)

The secondary objective of this study is to compare the differences in the following indicators between the test and control groups:

- Number of positive cases per 1,000 catheter-days of bacterial colonization at CVC tips
- Bacterial colonization rate at the tip of other types of (percutaneous) deep vein catheters and the catheterization site (number of culture positive cases/total catheters \times 100% and number of positive cases per 1,000 catheter-days), including hemodialysis, PICCO, float catheters, etc.

- Incidence rate of Central Line Associated Bloodstream Infections (CLABSI) or Catheter Related Blood Stream Infections (CRBSI)
- Type of pathogenic microorganism (G+/G-/fungal or specific species, drug-resistant bacteria, etc.) and percentage of positivity
- Securement performance of the dressing: Frequency of dressing changes associated with wear time and lift or drop-off
- Effects on the skin of the covered area, e.g. local infection, local skin irritation.

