2. Assessment of skin conditions around the catheter site, with reference to the standards for evaluating local skin irritation as listed in the appendix;

The following data will be collected during the follow-up visit:

1. Date and time of dressing change, site of dressing change, reason for dressing change. Scoring and assessment of edge curling in the case of dressing changes due to severely edge curling in the previous use;
2. Documentation of skin conditions around the catheter site, including erythema, edema, rash, etc., and scoring with reference to the standards for evaluating local skin irritation as listed in the appendix.
3. Any changes in medication use relevant to the trial, including mainly fat emulsions, heparin, blood transfusions and antimicrobial drugs;
4. Adverse events, device defects, complaints.

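### The SAP's group comparison of skin scores omits the dressing-change visits, prints erythema twice where edema is probably meant, and uses a different test from the protocol

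*SAP*

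**What the plan says.** Protocol 5.2 makes this a secondary objective: "Effects on the skin of the covered area, e.g. local infection, local skin irritation". SAP 4.2 lists it as a safety indicator.

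Protocol 10.2.3 requires, at follow-up (dressing-change) visits, "Documentation of skin conditions around the catheter site, including erythema, edema, rash, etc", scored on the appendix scales. Table 10.3-1 marks the skin assessment at Day 0, dressing-change visits, the end-of-treatment visit and withdrawal. Appendix B gives ordinal scales for erythema (0-4), edema (0-4) and itch (0-3).

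The analysis instruction is one sentence in SAP 6.4. It calls for a description of "erythema, erythema, pruritus score and skin infection at the baseline and last" visit, defines the last visit as "i.e., end of treatment or withdrawal discontinuation visit) visit at different insertion sites in two groups", and ends with "compare the two groups using the chi-square test or Fisher's exact test".

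Protocol 19.4 places skin condition among the results "such as wearing duration, frequency of replacement, skin condition, and number of deaths, will be analyzed using t-tests or rank sum tests accordingly".

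**The concern.** The SAP 6.4 sentence is the only planned between-group test of skin effects, and it raises three problems.

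- **Time points.** Dressing-change scores do not enter the comparison. Irritation seen at a change and gone by catheter removal leaves no trace in it.
- **Variables.** Followed literally, the sentence gives a programmer no instruction to compare edema.
- **Test.** The SAP and protocol name different tests for the same data. The SAP's choice ignores the order of the scores when the table is left uncollapsed.

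At stake is how well the trial can describe skin tolerance of the CHG dressing against the plain one. On a safety question, missed transient reactions and a less sensitive test both make a real difference harder to see.

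**Working it through.** The plan gives no figure for this analysis, so there is none to reproduce. The check is a comparison of texts, followed by two calculations of size.

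**1. Texts side by side**

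| Point | Collected or stated elsewhere | SAP 6.4 |
|---|---|---|
| Visits | Day 0, each dressing change, end of treatment, withdrawal (Protocol Table 10.3-1) | Baseline and last visit |
| Items | Erythema, edema, pruritus, skin infection (SAP 6.2.2) | Erythema, erythema, pruritus, skin infection |
| Test | t-test or rank sum (Protocol 19.4) | Chi-square or Fisher |

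SAP 6.2.2 has the same four items in the same order, with edema in second place, so the repeated word in 6.4 is most likely a slip. No section of the SAP text summarises or lists the dressing-change scores; the listing in 6.2.2 concerns skin evaluation before enrollment. Protocol 19.7 says that a change of method before data lock will be documented in the SAP. SAP section 9 records none.

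**2. Share of scheduled assessments left out**

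Let m be the number of interim dressing-change visits for a site. Assessments made: m + 2. Assessments used: 2.

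- Edema restored: unused share = m/(m + 2).
- Sentence read literally (two of three irritation scales, at two visits): unused share = 1 − 4/[3(m + 2)].

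| m | Edema restored | Literal reading |
|---|---|---|
| 0 | 0% | 33% |
| 1 | 33% | 56% |
| 2 | 50% | 67% |
| 3 | 60% | 73% |

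The documents do not give m. Protocol 10.2.3 guarantees one interim visit, on day 7, and only if the catheter stays longer than 7 days. Participation is about 3-14 days (Protocol 6.0).

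**3. Cost of the nominal test**

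From the documents: 220 per arm, two-sided 0.048 (SAP 3.2 and 6.1). Assumed: one independent score per subject, control distribution 80/12/5/2/1% over scores 0-4, and a proportional-odds shift with odds ratio 1.8.

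- Control cumulative odds: 0.80/0.20 = 4.0; 0.92/0.08 = 11.5; 0.97/0.03 = 32.3; 0.99/0.01 = 99.
- Divided by 1.8: 2.22, 6.39, 17.96, 55.0.
- Cumulative probabilities in the other arm, odds/(1 + odds): 0.690, 0.865, 0.947, 0.982. Its distribution is therefore about 69.0/17.5/8.3/3.5/1.8%.

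Simulated power: five-level chi-square about 53%, tie-corrected Wilcoxon about 76%. With an odds ratio of 1.6 the figures are about 35% and 56%. With no difference, both tests reject about 4 to 5% of the time, so the chi-square is valid.

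Three other assumed control distributions, at odds ratios 1.5 to 2.0:

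| Control share at score 0 | OR 1.5, chi-square / rank sum | OR 1.8 | OR 2.0 |
|---|---|---|---|
| 85% | 20% / 36% | 45% / 67% | 61% / 83% |
| 70% | 34% / 53% | 67% / 86% | 83% / 95% |
| 50% | 41% / 63% | 77% / 92% | 90% / 98% |

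The loss in this table is about 8 to 23 percentage points. If the score is instead collapsed to any versus no erythema, chi-square power in the 80% case at odds ratio 1.8 is about 75%, close to the rank-sum figure. The loss therefore belongs to the uncollapsed table, not to chi-square as such.

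**The case against.** **Adverse events provide another route, and it stands in part.** Erythema, edema, rash, itching and local infection are anticipated device effects (Protocol 3.3.2) and reportable (11.4). Adverse events are collected at each dressing change, and SAP 6.4 tabulates them by group, taking the most severe occurrence per participant. A reader might infer that transient reactions are not counted anywhere; the documents do not support that. But no rule turns a skin score into an adverse event, so low scores may never be reported as one, and no between-group test is named for adverse events.

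**Withdrawal visits count as last visits.** This stands. A subject who leaves because of a skin reaction has a skin assessment scheduled at the withdrawal visit, and it enters the comparison.

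**The protocol's sentence on tests is generic.** It puts deaths in the same t-test/rank-sum list and says the tests are used accordingly. That weakens the conflict, but skin condition is named and the SAP does not explain the departure.

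**The SAP fixes no table layout.** This stands. The power figures need the uncollapsed table and assumed distributions, and they ignore the SAP's presentation by insertion site. No power is claimed for skin endpoints.

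**By-visit listings may exist.** SAP section 9 puts tables and listings in a separate file, so they cannot be ruled out. A listing would still not be a planned comparison.

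**A worst-score summary has its own bias.** This stands. At an assumed 10% risk per assessment, the chance of at least one reaction is 1 − 0.9^k: 10%, 19% and 27% for k = 1, 2 and 3. The number of assessments may differ by arm, because dressing changes are themselves an outcome.

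**Conclusion.** The concern holds in limited form. The score comparison omits the dressing-change visits; as printed it does not compare edema; and its test departs from Protocol 19.4 without explanation. The first two points rest on the text alone. The sizes rest on assumptions: 33% or 50% of assessments unused with one or two interim visits and edema restored, and about 53% against 76% power for one assumed distribution and effect on a five-level table.

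Two stronger readings are tempting and should not be drawn. The first is that edema was deliberately dropped; SAP 6.2.2 makes a wording slip far more likely. The second is that most of the irritation data go unused. With edema restored that needs at least three interim visits per site, and the documents state no such number. For the same reason the documents give no basis for the proportion of reactions that would be missed.

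Severity is minor to moderate. The chi-square and Fisher tests are valid, skin infection as a yes/no item suits them, and the primary endpoint is not touched.

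**What to change.** Amend SAP 6.4 as follows.

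1. Replace the second erythema with edema, or state that edema is intentionally not compared and why.
2. Compare the ordinal erythema, edema and itch scores by Wilcoxon rank-sum, in line with Protocol 19.4. Keep chi-square or Fisher for skin infection (yes/no). If chi-square is preferred for the scores, state the grouping of categories and record the departure from the protocol.
3. Keep the last-visit comparison. Add a by-visit summary and, as a supplementary analysis, the worst post-baseline erythema, edema and itch score per subject, taken over all sites. One value per subject also avoids treating several sites in one patient as independent.
4. Report the number of skin assessments and sites per arm beside the worst score, since it rises with both.

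The cost is SAP wording and a few extra tables. The data are already collected, and neither the visits nor the sample size changes.
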